- Hypertension at Screening, defined as Hypertension (Standardised MedDRA Query [SMQ]) in the Medical History form: Yes or No
- Individual co-morbidities included in the Charlson Index: myocardial infarction (Yes or No), congestive heart failure (Yes or No), peripheral vascular disease (Yes or No), cerebrovascular disease (Yes or No), dementia (Yes or No), chronic obstructive pulmonary disease (Yes or No), connective tissue disease (Yes or No), peptic ulcer disease (Yes or No), liver disease ('None', 'Mild' or 'Moderate or Severe'), diabetes mellitus ('None or diet controlled', 'Uncomplicated' or 'End-organ damage'), hemiplegia (Yes or No), moderate or severe chronic kidney disease (Yes or No), solid tumor ('None', 'Localized' or 'Metastatic'), leukemia (Yes or No), lymphoma (Yes or No) or AIDS (Yes or No).
- ISARIC-4C mortality score: Low (0 3), Intermediate (4 8), High (9 14) or Very high (≥ 15)
- ISARIC-4C deterioration probability (%): `≤ 25', `(25 50]', or `> 50'
- Lactate dehydrogenase (LDH) at Baseline: ≤ ULN or > ULN

- CRP (mg/L) at Baseline: ≤ 100 or > 100
- D-dimer at Baseline: ≤ ULN or > ULN
- Ferritin at Baseline: ≤ ULN or > ULN
- Creatinine at Baseline: ≤ ULN or > ULN
- IL-6 at Baseline: ≤ Median or > Median value (at the analysis time cutoff may be updated based on distribution values if needed)
- IL-10 at Baseline: ≤ Median or > Median value (at the analysis time cutoff may be updated based on distribution values if needed)
- Lymphocytes count decreased at Baseline: 'Grade 0' or 'Grade  $\geq 1'$
- Neutrophils/lymphocytes ratio at Baseline:  $< 6 \text{ or } \ge 6$
- SARS-CoV-2 variant: Alpha, Beta, Gamma, Delta, Eta, Iota, Kappa, Lambda, Mu, or any potential new variant

The same covariates used for the primary efficacy endpoint analysis will be used for the subgroup analyses.

For ISARIC-4C mortality score and deterioration probability calculation:

- A Glasgow coma scale score of 15 is assumed for all the patients.
- Urea (mmol/L) will be calculated as blood urea nitrogen (mmol/L) \* 60 / 28.

Forest plots of the hazard ratios, and the 95% CI for the comparison of each dose of plitidepsin versus control arm will be presented by endpoint for all subgroups using the ITT population.

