#### 7.6.5 Exploratory Analysis

A multivariate analysis will be performed for the primary and key secondary efficacy endpoint, including the treatment group, randomisation stratification factors and all the above subgroup variables as covariates. Those covariates with more than 10% of missing values will be omitted from the multivariate analysis. A stepwise selection model will be used, with significant level equal to 0.2 and 0.05, to enter into the model and to remain in the model, respectively.Treatment group will be forced to be included in addition to the significant covariates.

Time-to sustained withdrawal of oxygen supplementation will be compared between each dose of plitidepsin versus control arm receiving the antiviral control arm, ie, the regulatory-approved antiviral for those patients randomised to the control arm (remdesivir or favipiravir).

Time-to sustained withdrawal of oxygen supplementation will be analysed using the Kaplan-Meier method and 25th percentile, median and 75th percentile time will be presented for the plitidepsin arms and control arm receiving the antiviral control

Sponsor Name: Pharma Mar S.A. Sponsor Protocol ID: APL-D-003-20

arm, together with 95% CIs. The 95% CIs will be computed based on Brookmeyer-Crowley method and using a log log transformation. The mean time to sustained withdrawal of oxygen supplementation and its standard error will be also presented for the pooled plitidepsin arms and control arm.

Time-to sustained withdrawal of oxygen supplementation between each dose of plitidepsin versus control arm receiving the antiviral control arm will be compared using a stratified log-rank test, including the randomisation stratification factors as covariates, ie, Geographical Region (Europe vs. Rest of the World), Charlson Comorbidity index (0-1 vs. >1) and pre-baseline Barthel index ( $\geq$ 90 versus <90) as derived using the eCRF data. The 2-sided p-values for the comparison of the pooled plitidepsin arms versus control arm will be presented.

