### 7.7.3 Laboratory Evaluations

Data for the haematology, serum chemistry, and coagulation analytes received from central laboratory will be listed and summarized by treatment group and overall plitidepsin, and visit. Haematology and serum chemistry analytes from local laboratories recorded at Screening in the eCRF will be listed only. If data for any additional analytes are also received then these will be listed only.

Immunology and Serological SARS CoV 2 data are summarised within the other secondary efficacy endpoints.

Haematology	Serum Chemistry	
Red Blood Cell Count	Alanine aminotransferase (ALT)	
Haemoglobin	Aspartate aminotransferase (AST)	
Haematocrit	Alkaline phosphatase	
White Blood Cell Count	Gamma-Glutamyltransferase (GGT)	
Neutrophils	LDH	
Eosinophils	Total Bilirubin	
Basophils	Direct Bilirubin	
Lymphocytes	Glucose (fasting)	
Monocytes	Sodium	
Platelet Count	Potassium	
Transunalagy	Calcium (adjusted)	
Immunology	Magnesium	
CRP	Blood Urea Nitrogen	
Ferritin	Creatinine	
IL-1β	Calculated Creatinine Clearance (Cockcroft-Gault equation)	
IL-6	Creatine Phosphokinase (CPK)	
IL-10	Albumin	
TNFa	Amylase	
	Lipase	
Other Samples	Procalcitonin	
Pregnancy tests (females	Troponin T	
only)	N-terminal pro-B-type natriuretic peptide (NT-pro-BNP)	
Coagulation	Serological SARS CoV 2 testing	
D-dimer	IgG	

All central Laboratory data will be reported in International System of Units. Local Laboratory data will be listed in the Units that they were collected in the eCRF. Outof-reference-range values will be flagged as high (H) or low (L) in the listings. For analysis purposes, values preceded by a "<" or a ">" sign (ie, those below or above the limits of quantification) will be considered equal to the lower or upper limit of quantification, respectively.

Central laboratory data will be summarized by visit using standard descriptive statistics by treatment group and overall plitidepsin for the As Treated population. Changes from Baseline will also be summarized. For post-Baseline, only data from scheduled visits will be included in the summary tables.

If more than 10% of the patients preform an unscheduled central laboratory assessment at the same relative day to the start date of study treatment then the central laboratory data will be also summarised at the specific relative day. In case of several unscheduled laboratory assessments at the same day we will use the worst result.

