### 6. APPENDIX 1. LABORATORY TESTS – PRECISION LEVELS

Category	Analyte	SI Unit	Precision
	-		(Decimal Point)
Haematology	RBC Count	Tl/L	1
Haematology	Haemoglobin	g/L	0
Haematology	Haematocrit	1	3
Haematology	WBC Count	G/L	1
Haematology	Neutrophils	%	1
Haematology	Abs. Neutrophils	Gl/L	2
Haematology	Eosinophils	%	1
Haematology	Abs. Eosinophils	Gl/L	2
Haematology	Basophils	%	1
Haematology	Abs. Basophils	Gl/L	2
Haematology	Lymphocytes	%	1
Haematology	Abs. Lymphocytes	Gl/L	2
Haematology	Monocytes	%	1
Haematology	Abs. Monocytes	Gl/L	2
Haematology	Platelet count	Gl/L	0
Chemistry	ALT(SGPT)	U/L	0
Chemistry	AST(SGOT)	U/L	0
Chemistry	Alkaline Phosphatase	U/L	0
	(ALP)		
Chemistry	GGT	U/L	0
Chemistry	LDH	U/L	0
Chemistry	Total Bilirubin	umol/L	1
Chemistry	Direct Bilirubin	umol/L	1
Chemistry	Glucose	mmol/L	1
Chemistry	Sodium	mmol/L	1
Chemistry	Potassium	mmol/L	1
Chemistry	Calcium (adjusted)	mmol/L	2
Chemistry	Magnesium	mmol/L	3
Chemistry	Creatinine	umol/L	1
Chemistry	Calculated Creatinine	mL/sec	1
	Clearance		
Chemistry	Albumin	g/L	0

Category	Analyte	SI Unit	Precision (Decimal Point)
Chemistry	Creatine Phosphokinase (CPK)	U/L	0
Chemistry	Troponin T	ng/L	2
Chemistry	NT-pro BNP	pmol/L	2
Chemistry	Blood Urea Nitrogen	mmol/L	1
Chemistry	Amylase	U/L	0
Chemistry	Lipase	U/L	0
Chemistry	Procalcitonin	ng/mL	3
Immunology	CRP	mg/L	1
Immunology	Ferritin	ug/L	1
Immunology	IL-1β	pg/mL	2
Immunology	IL-6	pg/mL	2
Immunology	IL-10	pg/mL	2
Immunology	TNFα	pg/mL	2
Coagulation	D-dimer	mg/L	3

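### The urea conversion for the ISARIC-4C scores applies a mass-unit factor (60/28) to values in mmol/L and so overstates urea 2.14-fold

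*SAP*

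**What the plan says.** Under the lead-in "For ISARIC-4C mortality score and deterioration probability calculation", SAP section 7.6.4 sets two rules. The first assumes a Glasgow coma scale score of 15 for every patient. The second is the urea conversion: "Urea (mmol/L) will be calculated as blood urea nitrogen (mmol/L) \* 60 / 28".

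The unit of the input is stated in two other places. Appendix 1 of the TFL shells (laboratory precision levels) has the row "Blood Urea Nitrogen mmol/L 1", that is, mmol/L to one decimal. Section 7.7.3 says: "All central Laboratory data will be reported in International System of Units". In the schedule of assessments (SAP Appendix 4, serum chemistry footnote), blood urea nitrogen is an on-study central laboratory test and is not among the local screening tests.

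Both scores are analysed in fixed categories: 0–3, 4–8, 9–14 and ≥15 for mortality, and ≤25, (25–50] and >50 for the deterioration probability. They are subgroup variables for the primary endpoint (section 7.6.4). They are also candidate covariates in the stepwise Cox models for the primary and key secondary endpoints, since section 7.6.5 enters "all the above subgroup variables as covariates". The post-hoc addendum keeps both scores in Tables 14.2.4.1.1 and 14.2.4.2.1 and in Figure 14.2.1.2.1, and refers the reader to SAP version 4.0 for further definitions. It does not change the urea rule.

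**The concern.** A factor of 60/28 is familiar from converting urea nitrogen to urea in mg/dL, where it is correct. Here it is applied to a molar concentration to give another molar concentration. Moles count molecules, and the mass of urea relative to its nitrogen plays no part.

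A constant scaling error would do no harm if the variable were split at its own median. ISARIC-4C is different: it is an externally defined score with fixed categories, so doubling one input can move a patient across a boundary. Section 2.1.3.3 makes the influence of deterioration risk scores a secondary objective, section 3.5 names ISARIC-4C, and section 7.6.2.3 says the subgroup analysis addresses that objective. If the rule is followed, the ISARIC-4C rows of the forest plot may carry risk labels that some patients do not merit, and the stepwise models would choose among covariates that include two distorted ones.

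**Working it through.** **Inputs.** Factor 60/28, with input and output both in mmol/L (SAP 7.6.4). BUN reported in mmol/L (TFL shells, Appendix 1), with central laboratory data in SI units (SAP 7.7.3). The figures 60 and 28 are the molar mass of urea and the mass of the two nitrogen atoms in one urea molecule.

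**Step 1: reproduce the plan's factor.** 60/28 = 2.143. Start from 1 mmol/L urea:
- urea mass = 1 × 60/10 = 6.0 mg/dL
- urea nitrogen mass = 1 × 28/10 = 2.8 mg/dL
- ratio = 6.0/2.8 = 2.143

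The factor reproduces exactly as a mass-to-mass conversion.

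**Step 2: test it on the stated units.** Keep true urea at 1 mmol/L and vary what the reported BUN figure might mean. The plan's output is that figure times 60/28.

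| Meaning of the BUN figure | BUN for 1 mmol/L urea | Plan's urea | Overstatement | Factor that would be right |
|---|---|---|---|---|
| mmol/L per urea molecule (one N₂ pair, 28) | 1.0 | 2.143 | 2.14-fold | 1 |
| mmol/L per single nitrogen atom (14) | 2.0 | 4.286 | 4.29-fold | 0.5 |
| Label wrong, data in mg/dL | 2.8 | 6.0 | 6-fold | 10/28 = 0.357 |
| Nitrogen mass divided by 60 and called mmol/L | 0.467 | 1.0 | none | 2.143 |

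The first row is the usual SI convention. The second is the other legitimate molar reading, and it makes the error larger. In the third row the result is urea in mg/dL, not the mmol/L that the rule promises. Only the fourth rescues 60/28. It is itself a mis-conversion, and the SAP states no such convention.

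**Step 3: size on the usual convention.**

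| True urea (mmol/L) | Urea under the plan's rule (mmol/L) |
|---|---|
| 3 | 6.4 |
| 5 | 10.7 |
| 7 | 15.0 |
| 10 | 21.4 |
| 15 | 32.1 |

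Every value rises by 2.143 − 1 = 114%.

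**Step 4: consequence for a threshold.** A patient is placed above a urea cut-point c whenever 2.143 × true urea exceeds c, that is, when true urea exceeds (28/60)c = 0.467c. All patients with true urea between 0.467c and c are therefore put on the wrong side, whatever c is. The SAP gives neither the urea cut-points nor the coefficients of the two scores, so the number of patients who change category cannot be derived from it. For a score that rises with urea, the movement is upward.

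**The case against.** The opposing case accepts that 60/28 is a mass ratio applied to molar units. It presses four limits.

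- **Convention.** The 2.14-fold figure depends on how the central laboratory defines BUN in mmol/L, which the SAP does not spell out. One reading, nitrogen mass divided by 60, would even make the factor right. This stands as a reason to ask the laboratory first and to say that no *standard* reading supports the rule. It does not defend the text, which describes no such convention.
- **Component versus category.** The analysis uses broad score categories, so a patient with the wrong urea may stay in the same one. This stands: some patients may be reclassified, not all.
- **Effect on hazard ratios.** Urea is used as a baseline variable and the rule is the same in every arm, so the randomised comparison within a mislabelled stratum is not thereby biased between arms. This stands too. The harm is that the strata are not the risk groups they claim to be. In the Cox models both scores may also drop out, through the 10% missing-data rule or the 0.2/0.05 selection levels.
- **Scope.** The primary and key secondary tests do not use urea. ISARIC-4C is absent from the key secondary subgroups (section 7.6.4) and the safety subgroups (section 7.7.7). This limits the importance of the error but does not remove it.

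**Conclusion.** The rule is wrong as written. With BUN in mmol/L counted per urea molecule, urea in mmol/L equals BUN in mmol/L, and the plan's rule overstates it 2.14-fold. Counted per nitrogen atom, the overstatement is 4.29-fold, so the range for genuine mmol/L data is 2.14 to 4.29. Neither the SAP nor the addendum corrects it elsewhere.

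Both ISARIC-4C variables are therefore derived from a wrong input, with an unknown number of patients moved to a higher category. The exposed outputs are the ISARIC-4C rows of the primary-endpoint forest plots (Figures 14.2.1.2 and 14.2.1.2.1) and the stepwise multivariate tables (14.2.4.1, 14.2.4.2, 14.2.4.1.1 and 14.2.4.2.1). The confirmatory results are untouched. The error should be corrected, but it does not threaten the trial's main conclusion.

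**What to change.** 1. Ask the central laboratory what its BUN figure in mmol/L counts, and check the unit in the analysis dataset.
2. If it is urea nitrogen per urea molecule, replace the line in section 7.6.4 by: urea (mmol/L) = BUN (mmol/L). If it counts single nitrogen atoms, multiply by 0.5. If the values prove to be mg/dL of urea nitrogen, multiply by 10/28 to reach mmol/L of urea.
3. Check which formula the program actually used. If it was 60/28, re-derive both ISARIC-4C variables from the locked data, re-run the forest plots and multivariate tables named above, and report how many patients changed category in each arm.
4. Record the correction and its reason in a dated note to the SAP and the addendum.

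The cost is one query to the laboratory, one line of text, one line of code and a re-run. No new data are needed.

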#### 7.6.5 Exploratory Analysis

A multivariate analysis will be performed for the primary and key secondary efficacy endpoint, including the treatment group, randomisation stratification factors and all the above subgroup variables as covariates. Those covariates with more than 10% of missing values will be omitted from the multivariate analysis. A stepwise selection model will be used, with significant level equal to 0.2 and 0.05, to enter into the model and to remain in the model, respectively.Treatment group will be forced to be included in addition to the significant covariates.

Time-to sustained withdrawal of oxygen supplementation will be compared between each dose of plitidepsin versus control arm receiving the antiviral control arm, ie, the regulatory-approved antiviral for those patients randomised to the control arm (remdesivir or favipiravir).

Time-to sustained withdrawal of oxygen supplementation will be analysed using the Kaplan-Meier method and 25th percentile, median and 75th percentile time will be presented for the plitidepsin arms and control arm receiving the antiviral control

Sponsor Name: Pharma Mar S.A. Sponsor Protocol ID: APL-D-003-20

arm, together with 95% CIs. The 95% CIs will be computed based on Brookmeyer-Crowley method and using a log log transformation. The mean time to sustained withdrawal of oxygen supplementation and its standard error will be also presented for the pooled plitidepsin arms and control arm.

Time-to sustained withdrawal of oxygen supplementation between each dose of plitidepsin versus control arm receiving the antiviral control arm will be compared using a stratified log-rank test, including the randomisation stratification factors as covariates, ie, Geographical Region (Europe vs. Rest of the World), Charlson Comorbidity index (0-1 vs. >1) and pre-baseline Barthel index ( $\geq$ 90 versus <90) as derived using the eCRF data. The 2-sided p-values for the comparison of the pooled plitidepsin arms versus control arm will be presented.

A stratified Cox proportional-hazards regression model, including the randomisation stratification factors as covariates, ie, Geographical Region (Europe vs. Rest of the World), and Charlson Comorbidity index (0-1 vs. >1) and pre-baseline Barthel index ( $\geq$ 90 versus <90) as derived using the eCRF data, will be applied to compare results between each dose of plitidepsin arms and control arm receiving the antiviral control arm. Hazard ratios, 95% CIs, and 2-sided p-values for the comparison of each dose of plitidepsin arms versus control arm receiving the antiviral control arm will be presented.

Similarly, time-to sustained withdrawal of oxygen supplementation will be compared between each dose of plitidepsin versus control arm without receiving the antiviral control arm.

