# 6.2 Handling of Dropouts, Missing Data, Intercurrent Events and Outliers

Patients with no available data for any time-to event efficacy endpoint will be censored at time 0.

For TFLs where calculation needs the first drug administration date, e.g. time between onset date of COVID-19 symptoms and initiation of study treatment (days), in patients randomized but not treated the randomization date will be used.

In the ISARIC-4 programming calculation a Glasgow coma scale score of 15 is assumed for all the patients.

Missing data, except dates, will not be imputed for safety analyses. The safety evaluations will be performed on observed data only.

For AEs with partial or missing onset or stop dates:

- AE stop date will be imputed first as:
  - If stop date is completely missing, assume it is ongoing (no imputation);
  - For a partial AE stop date:
    - day is missing, then take the last day of the month
    - both day and month are missing, then take December 31st.
  - If the imputed AE stop date is after the End of the Study date, then the stop date will be set to the End of the Study date.
- Then AE onset date will be imputed as:
  - If onset date is completely missing: the first dose date;
  - For a partial AE onset date
    - day is missing:

Sponsor Protocol ID: APL-D-003-20

- Partial date < the first dose date: last day of the month
- Partial date = the first dose date: the first dose date
- Partial date > the first dose date: first day of the month
- both day and month are missing, ie, only the year is available:
  - Partial date < the first dose date: December 31st
  - Partial date = the first dose date: the first dose date
  - Partial date > the first dose date: January 1st
- If the imputed AE onset date is after the AE stop date/imputed AE stop date, then the onset date will be set to the AE stop date/imputed AE stop date.

The imputed dates will not be listed. Study day relative to the first dose of study drug associated with missing or partial dates will not be displayed in AE listings.

In the event that a partial date (month/year or year) for concomitant medication is available, concomitant medication start and stop dates will be imputed as:

- When both month and year are available first day of the month will be used for start date and the last day of the month will be used for the stop date.
- When only year is available January 1st will be used for the start date and December 31st will be used for the stop date.

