# 8. Changes in Planned Analysis

Despite wording in Protocol that WHO score 0 requires a test with RNA undetected (which would be achieved with a PCR or similar test), as scarce cases have been reported, Pharma Mar is accepting negative antigen tests (which is a protein detection test, and not RNA detection test) qualifying for score of 0.

Recruitment was stopped due to slow recruitment before reaching the 33% of events by Pharma Mar decision and futility analysis was cancelled.

An exploratory analysis of the comparison of the primary efficacy endpoint between each dose of plitidepsin versus control arm receiving and not receiving the antiviral control arm, ie, the regulatory-approved antiviral for those patients randomised to the control arm (remdesivir or favipiravir), will be performed.

CONFIDENTIAL

An exploratory analysis of the prior primary efficacy endpoint based on protocol amendment v6 will be performed at the final analysis time due to some regulatory agencies request.

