### Table 14.2.4.1 Time to Sustained Withdrawal of Oxygen Supplementation - Multivariate Analysis (Intent-To-Treat Population)

Notes: Sustained withdrawal of oxygen supplementation (in days) with no subsequent reutilisation during remaining study period is defined as the first day, from randomisation through completion of the study, on which a patient

i. satisfies categories 0 to 4 on the 11-point WHO Clinical Progression Scale, and

ii. has no subsequent reutilisation of oxygen supplementation (5 to 10 on the 11-point WHO Clinical Progression Scale)

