[a] Parameter Estimate, Standard Error, p-value, and Hazard Ratio based on a Cox proportional-hazards regression model with treatment group, randomisation stratification factors, ie, geographical region (Europe, Rest of the World), Charlson Comorbidity Index (0 - 1, > 1) and pre-baseline Barthel index ( $\geq 90$  versus < 90) as derived using the eCRF data, and patients included before and after amendment (Protocol v.6 or before, Protocol v.7), sex (female, male), age at study entry (18 to 39, 40 to 64,  $\geq$  65 years), race (asian, black, white, other), ethnic group (Hispanic or Latino, Not Hispanic or Latino), site location (Site XXX, Site XXX, Other Sites), use of antiviral therapies or immunomodulatory drugs through the study (Yes, No), previous COVID-19 vaccination status (Fully vaccinated, Non-fully vaccinated), anti-SARS-CoV-2 IgG at Day 1 (Non-positive, Positive), pre-randomisation dexamethasone (Yes, No), total duration of corticoid therapy ( $\leq$  9 days, [9 - 11] days, > 11 days), total cumulative dose of corticoid therapy (dexamethasone or equivalent) ( $\leq$  60 mg, > 60 mg), SARS-CoV-2 viral load (log10 copies/mL) at Day 1 before study drug administration ( $\leq 4$ , [4 - 7], > 7), time between onset date of COVID-19 symptoms and initiation of study treatment ( $\leq 5$  days, 6 - 10 days, > 10 days), body mass index (kg/m2) at Screening (< 30,  $\geq$  30), hypertension at Screening (Yes, No), myocardial infarction (Yes, No), consective tissue disease (Yes, No), periptic ulcer disease (Yes, No), liver disease (Yes, No), cerebrovascular disease (Yes, No), dementia (Yes, No), thronic obstructive pulmonary disease (Yes, No), moderate or severe chronic kidney disease (Yes, No), solit tumor (None, Localized, Metastatic), leukemia (Yes, No), lymphoma (Yes, No), AIDS (Yes, No), ISARIC-4C mortality score (Low (0 - 3), Intermediate (4 - 8), High (9 - 14), Very high ( $\geq 15$ )), ISARIC-4C deterioration probability ( $\leq 25$ , (25 - 50], > 50), LDH at Baseline ( $\leq$  ULN, > ULN), creatinine at Baseline ( $\leq$  ULN, > ULN)

- The displayed xxx do not reflect actual decimal precision. Please follow Section 2.11 for rounding rules.
- Omit those covariates with more than 10% of missing values from the multivariate analysis.
- Force to include the treatment arm in addition to the significant covariates.

Variable	Parameter Estimate	Standard Error	p-value	Hazard Ratio

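### The exploratory stepwise Cox models are labelled ITT but, run as written, use only patients complete on every candidate covariate; the tables show no N or events, and the randomisation strata can be selected out

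*SAP*

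**What the plan says.** SAP section 7.6.5 plans a multivariate Cox analysis of the primary and the key secondary endpoint, "including the treatment group, randomisation stratification factors and all the above subgroup variables as covariates". The subgroup variables are those of section 7.6.4. On missing values it says: "Those covariates with more than 10% of missing values will be omitted from the multivariate analysis". On selection: "A stepwise selection model will be used, with significant level equal to 0.2 and 0.05", the first level to enter and the second to stay. On forced terms: "Treatment group will be forced to be included in addition to the significant covariates". The shell for Table 14.2.4.1 repeats this: "Force to include the treatment arm in addition to the significant covariates".

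The missing-data section (6.2) rules out imputation for one purpose only: "Missing data, except dates, will not be imputed for safety analyses". For model covariates there are a few specific rules. Glasgow coma score is set to 15 in the ISARIC-4C scores (6.2, 7.6.4). The randomisation date replaces the first-dose date in untreated patients (6.2, 7.4.3). Laboratory baseline is the last non-missing central value before first dose (7.7.3). No general rule is given, and the covariate levels listed under Table 14.2.4.1 include no 'missing' level.

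The tables are titled Intent-To-Treat, which section 5.1 defines as all randomised patients. Their columns are variable, parameter estimate, standard error, p-value and hazard ratio. The addendum repeats both models as Tables 14.2.4.1.1 and 14.2.4.2.1. Its programming notes take three post-baseline covariates out of the modelling: antiviral or immunomodulatory use, cumulative corticoid dose and corticoid duration.

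**The concern.** A covariate with up to 10% of its values missing stays a candidate. With no other rule set, a stepwise Cox fit excludes every patient who lacks a value on any candidate, including candidates that are later rejected. Many candidates are assay results or composites, so the analysed set can be smaller than the label says. Nothing in the table would show it, since neither N nor events appears.

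A difference between the adjusted treatment hazard ratio and the primary one could then reflect who was excluded and not the adjustment. The same problem affects comparison with the addendum's separate model of treatment and baseline IL-10 (Table 14.2.4.1.2), which may rest on different patients.

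Separately, because only treatment is forced in, the adjusted model may leave out the three factors by which randomisation was stratified.

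**Working it through.** The plan states neither a number of candidates nor an analysed N for these models, so there is no figure of its own to reproduce.

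**Candidates besides treatment** (sections 7.6.4 and 7.6.5, footnote of Table 14.2.4.1):

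- randomisation strata: 3
- protocol version: 1
- sex to hypertension, in the order listed: 15
- individual Charlson comorbidities: 16
- ISARIC-4C scores: 2
- baseline laboratory variables: 9
- virus variant: 1

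3 + 1 + 15 + 16 + 2 + 9 + 1 = 47. The addendum's programming notes remove 3, leaving 47 − 3 = 44 for the repeats, although the footnotes as printed still list the three.

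**Share of patients complete on k covariates, each missing a fraction m:**

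- independent gaps: (1 − m)^k
- no two gaps in the same patient (lower bound): max(0, 1 − k·m)
- fully overlapping gaps (upper bound): 1 − m

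The plan gives no missingness rates, so k and m are assumptions; the plan's only limit is m ≤ 10%. For k = 15 I took the assay or derived candidates: IgG, viral load, the nine laboratory variables, variant, body mass index and the two ISARIC-4C scores. k = 5 is a milder case.

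| m | k = 15, independent | k = 15, lower bound | k = 5, independent | full overlap |
|---|---|---|---|---|
| 1% | 86% | 85% | 95% | 99% |
| 2% | 74% | 70% | 90% | 98% |
| 5% | 46% | 25% | 77% | 95% |
| 10% | 21% | 0% | 59% | 90% |

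For example, 0.99^15 = 0.860 and 0.95^15 = 0.463.

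**Strata.** Section 7.6.1 stratifies the primary log-rank test, and its supportive Cox model, on region, Charlson and Barthel. Section 7.6.5 lists the same three as candidates but protects only treatment from removal. A stratum that does not enter at 0.2, or does not stay at 0.05, leaves the model.

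**The case against.** The strongest reply is about size. Most laboratory candidates come from the same Day 1 collection (Appendix 4), lymphocyte count and the neutrophil/lymphocyte ratio share a haematology result, and the ISARIC-4C scores use the chemistry urea. Gaps therefore probably cluster, which makes independence pessimistic. Sex, age, region and protocol version will hardly be missing. The specific rules for Glasgow score, symptom-to-treatment time and laboratory baseline close some gaps. All of this stands. It narrows the likely loss but does not bring it to zero or make it visible.

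A second reply is that a stepwise prognostic model may properly drop a factor that is not significant, and that the stratum-adjusted effect is already reported in section 7.6.1. That is fair, and it limits what is at stake. Still, keeping the design factors makes the adjusted hazard ratio comparable with the primary one at almost no cost.

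Some stronger readings are tempting but not supported:

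- That the models retain some 47 covariates. That is the v4.0 candidate pool; the stay level of 0.05 decides what remains.
- That almost nobody would be left. With all 47 candidates at the 10% ceiling and independent gaps, 0.7% would remain, but nothing in the plan suggests such rates.
- That the model has fewer than 175 events. Section 8 says "Recruitment was stopped due to slow recruitment before reaching the 33% of events", and section 7.8 sets that look at 175 events. But patients already enrolled are followed to Day 31, and no final event count is stated.
- That the plan forbids imputing covariates. It is silent on them; the prohibition in section 6.2 concerns safety data.

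**Conclusion.** The point holds, at minor severity. As written, the four stepwise tables would rest on complete cases across all candidates under an Intent-To-Treat title with no N or events, and the randomisation strata could be absent from the fitted model. This assumes that the usual complete-case default applies where the plan gives no rule.

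The size cannot be fixed from the document. Under full overlap the loss is at most 10%. With 15 independently incomplete covariates it would be 14% at 1% missing each and 54% at 5%.

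A reader might infer that the trial's main conclusions are at risk. They are not: these models are exploratory, and the primary and key secondary tests in sections 7.6.1 and 7.6.2.1 do not depend on them.

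**What to change.** In section 7.6.5 and the programming notes of the four tables:

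1. Force geographical region, Charlson index and Barthel index into the model together with treatment.
2. After selection, refit the chosen model on all ITT patients with the selected covariates observed. Optionally, give categorical factors a 'missing' level.
3. Print the N and events used in Tables 14.2.4.1, 14.2.4.2, 14.2.4.1.1 and 14.2.4.2.1.

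This costs a little more programming and needs no new data. The refit N may differ from the selection N, so report both. Multiple imputation before selection is possible, but it needs a rule for combining selections across imputed datasets. It is a debatable trade-off for an exploratory model, and I would not require it.
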